17.3.7 Additional clinical efficacy measures

Additional clinical efficacy measures will include:

- Each of the five individual components of ACR CRISS: mRSS (modified Rodnan skin score), FVC % predicted, HAQ-DI (Health Assessment Questionnaire-Disability Index), PtGA (Patient Global Assessment), MDGA (Physician Global Assessment)
- DLCO % predicted
- HRCT chest scan ILD severity using the Goh scoring method [6].
- Additional patient reported outcome Mahler Baseline/Transitional Dyspnea Index (Mahler BDI/TDI).

The additional clinical efficacy measures will be applied study day 1 (using FVC % predicted and DLCO % predicted at screening visit within 21 days), day 84 (week 12) and day 168 (week 24) except for HRCT chest which will be done at screening and day 168 (week 24). For the extension study the additional clinical efficacy measures will be applied study day 84 (week 36) and day 168 (week 48) except for HRCT chest which will be done only study day 168 (week 48).

Study Measures for the Exploratory Objective Assessing the Effects of Ixazomib on both Adaptive and Innate Immunopathogenesis of Scleroderma

17.4.1 Blood samples

17.4.1.1 Clinical Immunology Lab Assessments.

In addition to serum protein immunoelectrophoresis, quantitative immunoglobulins (IgG, IgA, IgM), and IgG tetanus toxoid titer included in 17.2.3 Study Measures for the Primary

Objective to Assess the Safety and Tolerability of Ixazomib, additional clinical laboratory immunology testing includes serum antinuclear antibody (ANA) titer; antibody titers to extractable nuclear antigens ENA (inclusive of Scl-70), centromere antibody, and RNA polymerase III; and rheumatoid factor titer for Exploratory Objectives.

Blood samples will be collected at screening visit, study day 1, day 28 (week 4), day 56 (week 8), day 84 (week 12), day 112 (week 16), day 140 (week 20), day 168 (week 24), and at the concluding follow-up study day 196-203 (week 28-29) for participants not proceeding on to the extension study. For the extension study, blood samples will be collected at study day 84 (week 36), day 168 (week 48), and at the concluding follow-up study day 196-203 (week 52-53) office visits..

17.4.1.2 Immunology Research Lab Tests

Blood samples will be obtained to further characterize known markers, explore novel markers of SSc-ILD [153-155], explore other pathways and markers, assess changes in these markers before and after initiation of ixazomib treatment, and further elucidate disease pathobiology and the effects of ixazomib.

Blood (maximum of 40 ml blood in 4 ACD tubes for flow cytometric analysis and serum preparation, one PaxGene tube for RNA and one acid-citrate-dextrose tube for DNA) will be collected at screening visit and study day 1 as baseline samples. Blood samples will also be collected at study day 28 (week 4), day 56 (week 8), day 84 (week 12), day 112 (week 16), day 140 (week 20), day 168 (week 24), and at the concluding follow-up study day 196-203 (week 28-29) office visits for participants not proceeding on to the extension study. For the extension study, blood samples will be collected at study day 84 (week 36), day 168 (week 48), and at the concluding follow-up study day 196-203 (week 52-53) office visits.

Whole blood will be stained for the assessment of immune cell phenotypes of subsets of DCs (pDCs, CD1c+ mDCs, CD141+ mDCs), B cells (naïve, memory, plasmablasts, plasma cells, marginal zone (MZ)-like, subsets of transitional B cells, B10-like, B1), CD4+ T cells (naïve, memory, TH1, TH2, TFH, and Tregs), CD8+ T cells (naïve and memory), NK and NKT cells, innate lymphoid cells (ILCs; ILC1, ILC2, ILC3) [156], and granulocytes (neutrophils, basophils, and eosinophils). The frequency of individual subsets of circulating immune cells as well as their activation status will be assessed.

Whole blood transcriptomics will be assessed by RNA-seq and/or Nanostring assay with selected genes. Planned analyses include IFN and B cell signatures (including BLIMP-1 and plasma cell signatures [116] as well as other potential biomarkers of scleroderma [153, 154], including TGF-beta, connective tissue growth factor, IL-6, CCL2, CXCL4, SP-D, CCL18, IFN-inducible chemokines (CXCL10 and CXCL11), adhesion molecules (ICAM-1, P-selectin, VCAM-1, and E-selectin), vascular biomarkers (including VEGF, endothelin-1, thrombomodulin, BNP, endostatin, and plasminogen), and VEGF [153].

Peripheral blood mononuclear cells (PBMCs) will be isolated by gradient centrifugation and used for further characterizing immune cell phenotypes. CD4+ T cell cytokine expression (IFN γ for TH1, IL-4/IL-5/IL-13 expression for TH2, FOXP3/CD25/IL-10/CTLA-4 expression for Tregs,

IL-21 expression for TH21, and IL-17 expression for TH17) and CD8+ T cell functions (Granzyme and cytokine expression), B cell expression of CD80, CD86, CD95, IL-6, IL-10, IL-6R, IL-21R, and TGF-beta), monocyte (CD14+CD16-, CD14+CD16hi, CD14-CD16hi) expression of IL-10, TGF-beta and IL-10 will be assessed by intracellular staining and flow cytometry. The amount of cytokines and chemokines expressed by specific cell types or by total PBMCs can also be assessed by bead-based multiplex assays.

Sera will be prepared and used for assessing serum scleroderma biomarkers. Planned analyses include cartilage oligomeric matrix protein (COMP); activity biomarkers CCL2 (MCP-1), BAFF, APRIL, and adiponectin; severity markers TGF-beta, IL-6 levels, IFN-inducible chemokine score (CXCL10 and CXCL11); predictive markers CXCL4 and CCL18; and semaphorin 3E, measurable circulating proteasomes and *Siglec-1* IFN expression.

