1.5 Innate Immune System – Plasmacytoid Dendritic Cells

As part of the innate immune system, pDCs are considered to be the main source of type-1 IFN in scleroderma skin [11, 41, 44]. These cells are largely responsible for the IFN gene

expression signature observed in scleroderma which is present even before overt skin fibrosis [32]. PDCs can be activated by endogenous inducers including several autoantigens and autoantibodies [11, 41]. Serum containing Scl-70 (topoisomerase 1) antibody significantly induced higher levels of IFN- α as compared with other autoantibodies. The production of IFN- α was greater in patients with diffuse cutaneous as compared with more limited cutaneous illness, as well as being greater in patients with ILD.

PDCs in both scleroderma skin and blood also secrete chemokine CXCL4 /platelet factor 4 (PF-4) [45]. CXCL4/ PF4 levels are elevated in both the skin and serum in scleroderma, and further potentiate the ability of pDCs to secrete IFN- α [46]. In bleomycin-induced skin fibrosis model, depletion of pDCs attenuated skin fibrosis as well as the associated IFN-1 signature and CXCL4 expression [46].

PDCs additionally have been shown to induce plasmablast differentiation into Ig-secreting plasma cells through a sequential cooperation of the two secreted cytokines IFN- α and IL-6 [47].

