6.3 Exploratory Objectives

To determine the immunologic effects of ixazomib 4 mg taken orally on days 1, 8, and 15 of a 28-day treatment cycle repeated for 6 cycles when administered to adult patients with scleroderma-related ILD as assessed by:

1. Skin biopsies for histology, immunohistochemistry, gene expression (RNA-seq), and proteomics analysis related to plasma cells, pDCs, mDCs, and macrophages; cytokines including IFN and IFN gene signature; and scleroderma biomarkers.
2. Whole blood samples for flow cytometric analysis of immune cells including subsets of dendritic cells, monocytes, T-cells, B-cells, eosinophils, mast cells, and other immune cells, including innate lymphoid cells (especially ILC2); and whole blood transcriptome analysis.
3. Serum for cytokine and chemokine analysis including IL-6, IFN, and related cytokine levels; scleroderma-related autoantibody diversity and titers, and scleroderma biomarkers.

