9.2 Ixazomib Dose Modification or Interruption

9.2.1 Management of Clinical Events

Adverse drug reactions such as thrombocytopenia, diarrhea, fatigue, nausea, vomiting, and rash have been associated with ixazomib treatment. Further details of management of ixazomib AEs are described in the ixazomib IB [143].

Ixazomib dose modification or interruption will be allowed for safety or tolerability reasons at any time during the study at the discretion of the investigator. In general, if dose modification is necessary, the first ixazomib dose reduction is to 3 mg; second dose reduction is to 2.3 mg; and thereafter, to discontinue use.

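### Research serum is to be prepared from ACD anticoagulant tubes and no clot tube is listed, so the exploratory serum markers would be plasma results labelled as serum

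*Combined protocol and SAP*

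**What the plan says.** Section 17.4.1.2 (Immunology Research Lab Tests) gives the tube list in its sentence on the screening and day 1 baseline samples: "maximum of 40 ml blood in 4 ACD tubes for flow cytometric analysis and serum preparation", then "one PaxGene tube for RNA and one acid-citrate-dextrose tube for DNA". No other tube is named for this draw.

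The same section then sets out what the blood is for. "Whole blood will be stained for the assessment of immune cell phenotypes", and "Peripheral blood mononuclear cells (PBMCs) will be isolated by gradient centrifugation". It also says: "Sera will be prepared and used for assessing serum scleroderma biomarkers". The serum list covers COMP, CCL2, BAFF, APRIL, adiponectin, TGF-beta, IL-6, CXCL10, CXCL11, CXCL4, CCL18, semaphorin 3E, circulating proteasomes and Siglec-1.

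Section 6.3 makes serum the specimen for the third exploratory objective: "Serum for cytokine and chemokine analysis including IL-6, IFN, and related cytokine levels", along with autoantibodies and scleroderma biomarkers. The visit lists in sections 18 and 25.2 mention only a blood sample for biomarkers and name no tube or matrix.

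**The concern.** Serum is what remains after blood has clotted. Acid-citrate-dextrose stops clotting, so the fluid taken from an ACD tube is plasma, diluted by the additive. The documents do not say this; it is general laboratory knowledge. On that basis the tube instruction and the specimen named in the objective do not match.

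Two things are at stake. The first is labelling and comparability. Sections 1.5, 1.6, 1.7 and 1.9 justify CXCL4, IL-6, CCL18, BAFF and APRIL with findings in patients' serum. Levels measured in citrated plasma but reported as serum could not be set directly beside those findings.

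The second is change from baseline. Section 17.4.1.2 aims to compare markers before and after ixazomib starts, and all 12 participants receive the drug. With no untreated control, a change of tube type between visits could not be told apart from a drug effect.

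**Working it through.** The plan states no figure to reproduce, so the check sets the tube list against what the assays need.

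**1. Tubes listed (17.4.1.2)**

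| Tube | Number | Stated use | Yields serum? |
|---|---|---|---|
| ACD | 4 | Flow cytometry and serum | No |
| PaxGene | 1 | RNA | No |
| ACD | 1 | DNA | No |

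Total 4 + 1 + 1 = 6 tubes. ACD tubes 4 + 1 = 5. Clot tubes 0.

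**2. Conflict within the shared tubes.** The four ACD tubes must supply whole blood for staining, which has to be unclotted, and serum, which has to come from clotted blood. One tube type cannot do both without a further step, such as reversing the citrate. The text supplied describes no such step and nowhere permits plasma in place of serum.

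**3. What is affected.** The serum list in 17.4.1.2 has 14 entries, counting CXCL10 and CXCL11 separately. The clinical antinuclear, Scl-70, centromere, RNA polymerase III and rheumatoid factor tests are specified separately in 17.4.1.1. The immunoglobulins and tetanus titer are in 17.2.3, which assigns all clinical tests to the institution's clinical laboratory. None of these uses the research tubes. Staining, mononuclear cells, RNA and DNA do not need serum.

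**4. Number of draws, if the baseline tube list also applies later.** Screening, day 1 and days 28, 56, 84, 112, 140 and 168 make 8.
- Participants who complete the main study and do not enter the extension add the day 196-203 follow-up: 8 + 1 = 9.
- Participants who complete the extension skip that visit and add extension days 84, 168 and 196-203: 8 + 3 = 11.

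**5. Two markers for which serum is not the obvious remedy.** Section 1.5 identifies CXCL4 as platelet factor 4: "PDCs in both scleroderma skin and blood also secrete chemokine CXCL4 /platelet factor 4 (PF-4"). Section 9.2.1 states: "Adverse drug reactions such as thrombocytopenia, diarrhea, fatigue, nausea, vomiting, and rash have been associated with ixazomib treatment". Clotting releases platelet contents into serum, so a serum CXCL4 level would depend partly on the platelet count, which the drug can lower. TGF-beta is also sensitive to platelet release. The release mechanism and the TGF-beta point are general laboratory knowledge, not statements in the protocol. Section 17.2.3 already schedules hematology with a platelet count at all 9 or 11 of the draws in step 4.

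**6. Volume.** 40 ml / 4 tubes = 10 ml per tube, assuming equal tubes and that the maximum refers to those four. Replacing one leaves 40 − 10 = 30 ml of anticoagulated blood from this set.

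**The case against.** The strongest reply is that this is a wording slip with little consequence. Most of the listed analytes can be assayed in citrated plasma. The stated purpose is change within patients before and after treatment, and a matrix held constant supports that, whatever its name. No numerical comparison with published serum levels is planned. Several of the same markers are also planned as whole-blood or skin transcripts, and plasmacytoid dendritic cells are stained directly. Section 24.2 rules out formal testing, and sections 24 and 25.5 contain no biomarker analysis. Appendix A, cited in section 19.0, is not in the text supplied, and a laboratory manual might name a serum tube.

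Much of this stands, and it limits the point. A reader might infer that the markers cannot be measured at all. The documents do not support that: the likely outcome is a plasma result under a serum label. A reader might also infer that, as planned, a platelet fall would appear as a CXCL4 fall through release on clotting. That mechanism belongs to serum, which the listed tubes would not produce, so putting a number on it would not measure this defect. It matters only for choosing the remedy. Nor do the documents show that any laboratory has switched tubes between visits; that is a risk created by an instruction that cannot be followed literally.

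What does not stand is that nothing needs changing. Transcripts are a different readout from circulating protein. Even if another document names a clot tube, section 17.4.1.2 would contradict it.

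**Conclusion.** The specimen instruction in section 17.4.1.2 is wrong as written. Its effect is mislabelling and loss of direct comparability with the cited serum findings, for the research serum markers in objective 6.3(3) only. The clinical autoantibody titers within that objective survive, and the primary and secondary objectives are untouched.

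It should be corrected because the change is small and baseline samples cannot be redrawn once dosing has started. The conclusion assumes that ACD has its usual anticoagulant meaning, which the spelled-out name in the same sentence supports, and that no document outside the text supplied overrides the tube list. The count of 9 or 11 draws further assumes that the baseline tube list carries over to later visits, which the section does not restate.

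**What to change.** In section 17.4.1.2:

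- Replace one of the four ACD tubes with a plain clot (serum) tube at every research draw from screening onward, keeping the 40 ml maximum. State its volume and processing, and say that the tube list applies at all visits.
- Run the listed serum assays from that tube, except CXCL4 and TGF-beta. Measure those two in platelet-poor plasma from a remaining ACD tube, and show them against the same-visit platelet count.
- Fix one matrix per analyte for all visits, and align the wording of objective 6.3(3) with the two plasma markers.
- For samples already drawn, record the matrix actually used and do not mix matrices within a patient's change from baseline. A patient whose baseline is ACD plasma should be followed in ACD plasma for that comparison.

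Relabelling everything as ACD plasma would be simpler and would cure the mislabelling, but would leave the results not directly comparable with the serum findings in the rationale.

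The cost is a short text change and one tube in the kit, with the same venepuncture and total volume. The downside is about 10 ml less anticoagulated blood for cell work, on the equal-tube assumption. The platelet counts need no extra sampling.

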17.4.2 Skin Biopsies

Samples collected in this study will be used to further understand the potential impact of ixazomib on SSc. Two standard paired 5 mm forearm skin punch biopsies will be obtained on study day 1, day 84 (week 12) and day 168 (week 24). For the extension study, two standard paired 5 mm forearm skin punch biopsies will be obtained on study day 168 (week 48).

Histology will be performed to characterize the pathology outlines of scleroderma.

Immunohistochemistry will be performed to examine immune cell infiltration. Planned analyses include subsets of DCs (especially pDCs), macrophages (especially M2 macrophages; CD163+CD204+) [66, 89, 157], B cells, and ILCs (especially ILC2). Cytokine expression including IFN- α , IL-6, and TGF-beta) will also be assessed.

Transcriptomics of skin biopsies will be assessed by performing RNA-seq experiments in the Genomics Core in Mayo Clinic. Planned analyses include type 1 IFN and plasma cell gene signatures as well as collagen genes COL1A1, COL3A1, and COL5A1; CCL2, IL-6, CCL18, POSTIN, ENPP2, α -smooth muscle actin, COMP, pSTAT3; and semaphorin 3E. CCL3, IL-7, IL-13, and IFNy transcripts have been also increased in skin biopsies of scleroderma [158].

Tandem Mass Tag Proteomic analysis of skin biopsies will be performed at the Proteomics Core in Mayo Clinic. Planned analyses include quantitative measurement of >6,000 proteins expressed in skin biopsies collected before and after ixazomib treatment.

18.0 STUDY ASSESSMENTS BY VISIT

The results of all assessments and procedures listed below will be documented in the patient's medical record and recorded in the study records. To the extent possible, a patient's visits will be scheduled at the same time of day.

18.1 Washout Period (\leq 90 days)

A Washout Period will be required for the following patients:

- Patients not on background SSc-ILD medication at study Day 1:**

Washout will be required for those patients on an SSc-ILD medication other than MMF (See 8.2.4 Eligibility Criteria Medication Exclusions); those on an excluded

medication (See 8.2.4 Eligibility Criteria Medication Exclusions); and those who smoked tobacco in the 3 months before screening.

- **Patients on background stable oral dose of MMF at study Day 1:**

Washout will be required for patients on an excluded medication (See 8.2.4 Eligibility Criteria Medication Exclusions) and those who smoked tobacco in the 3 month (90days) before screening.

For those patients requiring medication washout, written informed consent will be obtained and a complete medical history will be taken (including systems review and prior and concomitant medications). The duration of washout will be 28 days for an investigational drug, 3 months (90 days) for tobacco smoking, and at least 5-half-lives for other medications. The number of study candidates needing to wash out medications other than MMF is anticipated to be very low based on the low prevalence of medicines other than MMF used clinically for the treatment of scleroderma-ILD. No study candidate already taking MMF will be asked to wash out MMF.

An HRCT chest scan will be used at screening to confirm eligibility. During the medication washout period, a request will be made to review a participant's previous HRCT chest scan. A HRCT chest scan may be used for this purpose if previously completed within 3 months prior to the date of written informed consent at either washout or screening, as applicable. The HRCT must demonstrate features consistent with SSc-ILD as confirmed following review of the HRCT images by Mayo radiology study staff. If the previous HRCT chest study is determined to be technically inadequate or cannot be made available for review by Mayo radiology study staff, or if the HRCT chest scan was performed more than 3 months prior to signing of written informed consent, a HRCT chest scan will be obtained during study screening.

During the medication washout, study procedures that will be performed during screening at the end of washout will be scheduled.

Participants unable to wash out other SSc-ILD medications and any excluded medications within the specified time frames will be considered ineligible to continue in the study.

18.2 Screening Period (Days -21 to-1)

During screening, which can last \leq 21 days, the following assessments and procedures will be performed:

1. For patients who do not require medication washout, written informed consent will be obtained before any assessments or procedures are performed.
2. Medical history, as follows:
 - a. **For patients who do not require medication washout:** complete medical history including systems review and prior and concomitant medications
 - b. **For patients who require medication washout:** directed medical history including a review of AEs/SAEs and concomitant medications that have been taken since the preceding visit.
 - c. An inventory of baseline symptoms, including those associated with background therapy if using MMF
3. Physical examination, including vital signs (blood pressure, heart rate, and

respiratory rate), body weight (in kilograms), and height (in centimeters)

4. mRSS
5. UCLA SCTC GIT 2.0 questionnaire
6. Hematology and serum chemistry blood samples
7. Clinical Immunology Tests blood sample
8. Serum pregnancy test (women of childbearing potential)
9. Blood sample for biomarker analyses
10. 12-lead ECG
11. Complete pulmonary function tests including lung volumes and DLCO % predicted
12. HRCT chest scan.
A HRCT chest scan will be used at screening to confirm eligibility. A HRCT chest scan may be used for this purpose if previously completed within 3 months prior to the date of written informed consent at either medication washout or screening, as applicable. The HRCT must demonstrate features consistent with SSc-ILD as confirmed following review of the HRCT images by Mayo radiology study staff. If the previous HRCT chest study is determined to be technically inadequate or cannot be made available for review by Mayo radiology study staff, or if the HRCT chest scan was performed more than 3 months prior to signing of written informed consent, a HRCT chest scan will be obtained during study screening.
13. Resting transthoracic echocardiogram only if not done within 6 months prior to written informed consent.

18.3 Treatment Period (Study Days 1-168)

18.3.1 Study Day 1

If the participant is confirmed to be eligible based on screening the following procedures will be performed on study Day 1:

1. Directed medical history including review of AEs/SAEs and concomitant medications that have been taken since the preceding visit.
2. Physical examination, including vital signs (blood pressure, heart rate, and respiratory rate), body weight (in kilograms).
3. If participant is taking background MMF, confirm dose and timing of dosing.
4. mRSS
5. UCLA SCTC GIT 2.0 questionnaire
6. Disease-status scales:
 - a. Mahler BDI
 - b. SHAQ
 - c. PtGA
